- Any other adverse event that, based upon appropriate medical judgment, may jeopardize the subjects' health and may require medical or surgical intervention to prevent one of the other outcomes listed in this definition.

Prolonged Hospitalization or Surgery Protocol – any AE that results in prolonged hospitalization should be documented and reported as a SAE. Any condition responsible for surgery should be documented as an AE if the condition meets the criteria for an AE. Neither the condition, prolonged hospitalization nor surgery are reported as an AE in the following circumstances:

- Prolonged hospitalization for diagnostic or elective surgical procedures for a preexisting condition. Surgery should not be reported as an outcome of an AE if the purpose of the surgery was elective or diagnostic and the outcome was uneventful.
- Prolonged hospitalization for required to allow efficacy measurement for the study.

An Unanticipated Problem (UP) is any incident, experience or outcome involving risk to subjects or others in any human subjects research that meets all of the following criteria:

- Unexpected (in terms of nature, severity or frequency) given (a) the research procedures that are described in the IRB-approval protocol and informed consent document, and (b) the characteristics of the subject population being studied;
- Related or possibly related to participation in such research (i.e., there is a reasonable possibility that the incident, experience or outcome may have been caused by the procedures involved in such research); and
- Suggests that the research places subjects or others at a greater risk of harm (including physical, psychological, economic or social harm) than was previously known or recognized

A Suspected Adverse Reaction (SAR) is any AE for which there is a reasonable possibility that it was caused by the drug. Reasonable possibility means that there is evidence to suggest a causal relationship between the drug and the AE. Examples of reasonable possibility are:

- A single occurrence of an event that is uncommon and known to be strongly associated with drug exposure.
- One or more occurrences of an event that is not commonly associated with drug exposure, but is otherwise uncommon in the

population exposed to the drug. • An aggregate analysis of specific events observed in a clinical trial that indicates that those events occur more frequently in the drug treatment group than in a concurrent or historical control group.

Investigator Reporting Requirements

The Principal Investigator will report all AEs and SAEs to the IND sponsor within 48 hours of becoming aware of the event. The report to the IND sponsor will include the study investigator's preliminary assessment of seriousness, severity and relatedness to the investigational product.

To IRB: Unanticipated Problems (UPs) must be reported promptly, but not later than 7 calendar days following the occurrence of the UP or the Principal Investigator's acquiring knowledge of the UP.

To DSMB: Serious adverse events not constituting an unanticipated problem is to be reported to the DSMB and the IND sponsor. Reporting should occur within 48 hours of knowledge of the SAE occurrence.

IND Sponsor Reporting Requirements

The IND sponsor will report the following SARs to the FDA: • To the FDA, as soon as possible, but no later than 7 calendar days after the SI's initial receipt of the information, any unexpected fatal or life-threatening SAR. • To the FDA and all participating investigators, as soon as possible but no later than 15 calendar days after the S-I determines that information qualifies for reporting, in an IND safety report, any SAR that is both serious and unexpected. • To the FDA and all participating investigators, as soon as possible but no later than 15 calendar days after the S-I determines that the information qualifies for reporting, any findings from epidemiological studies, pooled analysis of multiple studies or clinical studies, whether or not conducted under an IND or by the S-I, that suggest a significant risk in humans exposed to the drug. • To the FDA and all participating investigators, as soon as possible, but no later than 15 calendar days after the S-I determines that the information qualifies for reporting, any findings from animal or in vitro testing, whether or not conducted by the S-I, that suggest a significant risk in humans exposed to the drug. • To the FDA and all participating investigators, as soon as possible, but no later than 15 calendar days after the S-I determines that the information qualifies for reporting, any clinically important increase in the rate of a Serious SAR over that listed in the protocol or Investigator Brochure. • Expected SAEs and AEs should be included in the IND Annual Reports.

Follow-up information to a safety report will be submitted as soon as the relevant information is available. However, if the results of a sponsor's investigation show that an adverse drug experience not initially determined to be reportable are so reportable, the sponsor must report such experience as soon as possible, but no later than 15 calendar days after the determination is made.

SAFETY OVERSIGHT

Monitoring Plan

1. All AEs and SAEs will be reviewed by the study team in real time.
2. A data safety monitoring board (DSMB), composed of independent experts without conflict of interests will be established. The Board will review the study before initiation and quarterly thereafter.

The Board will review study data to evaluate the safety, efficacy, study progress, and conduct of the study.

Study monitoring

As per ICH-GCP 5.18 and FDA 21 CFR 312.50, clinical protocols are required to be adequately monitored by the study sponsor. Monitors will verify that

- (1) There is documentation of the informed consent process and signed informed consent documents for each subject
- (2) There is compliance with recording requirements for data points
- (3) All SAEs are reported as required
- (4) Individual subjects' study records and source documents align
- (5) Investigators are in compliance with the protocol
- (6) Regulatory requirements as per Office for Human Research Protections (OHRP), FDA, and applicable guidelines (ICH-GCP) are being followed.

Halting Criteria for the Study

The study enrollment and dosing will be stopped and an ad hoc review will be performed if any of the specific following events occur or, if in the judgment of the study physician, subject safety is at risk of being compromised:

- 1. Unexpected death of a dosed subject in relation to infusion
- 2. Occurrence of a life-threatening allergic/hypersensitivity reaction (anaphylaxis), manifested by bronchospasm with or without urticaria or angioedema requiring hemodynamic support with pressor medications or mechanical ventilation.
- 3. One subject with an unexpected SAE associated with study product.
- 4. Two subjects with a Grade 3 or higher toxicity for the same parameter associated with study product.
- 5. An overall pattern of symptomatic, clinical, or laboratory events that the medical monitor, ISM, or SMC consider associated with study product and that may appear minor in terms of individual events but that collectively may represent a serious potential concern for safety.
- 6. Any other event(s) which is considered to be a serious adverse event in the good clinical judgment of the responsible physician. This will be appropriately documented.

Furthermore, given that ADE may be an issue with convalescent antibody treatment, out of an abundance of caution we will monitor the number of subjects in each trial arm that progresses to an indication for need of mechanical ventilation. In monitoring the number of subjects that progresses to this stage, we will present these data to the DSMB and a masked outcomes assessor so that they may objectively evaluate and determine whether they would like to be unmasked. After at least 50% of trial participants have accumulated follow-up, the number of subjects that progress to this stage will be presented to the masked outcomes assessor and formally asked whether they (1) see a clinically meaningful difference between trial arms and (2) if so do they require a formal interim analysis. At any point should the DSMB require a formal interim analysis, we will examine the difference in treatment arms for need for mechanical ventilation. This interim analysis will adjust for factors related to need for mechanical ventilation including age and presence of cardiopulmonary comorbidities.

Upon completion of this review and receipt of the advice of the DSMB, the IND sponsor will determine if study entry or study dosing should be interrupted or if study entry and study dosing may continue according to the protocol. Should the trial not be stopped at this time point, the final analysis would

need to account the number of interim analyses that were conducted. Therefore, we would penalize any final analysis dividing our 0.05 alpha in half for each interim analysis.

REFERENCES

- Arabi, Y. M., Hajeer, A. H., Luke, T., Raviprakash, K., Balkhy, H., Johani, S., . . . Alahmadi, M. (2016). Feasibility of Using Convalescent Plasma Immunotherapy for MERS-CoV Infection, Saudi Arabia. *Emerg Infect Dis*, 22(9), 1554-1561. doi:10.3201/eid2209.151164
- Austin, P. C., & Fine, J. P. (2017). Practical recommendations for reporting Fine-Gray model analyses for competing risk data. *Stat Med*, 36(27), 4391-4400. doi:10.1002/sim.7501
- Casadevall, A., & Pirofski, L. A. (2003). Antibody-mediated regulation of cellular immunity and the inflammatory response. *Trends Immunol*, 24(9), 474-478. doi:10.1016/s1471-4906(03)00228-x

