1. Cumulative incidence of grade 3 and 4 adverse events during the study period
2. Cumulative incidence of serious adverse events during the study period

Secondary Objectives:

1. To compare duration of need for supplemental oxygen and/or mechanical ventilation between recipients of the anti-SARS-CoV-2 plasma and control plasma.
2. To compare duration of hospitalization between recipients of the anti-SARSCoV-2 plasma and control plasma.
3. To compare in-hospital and 28-day mortality between recipients of the anti-SARS-CoV-2 plasma and control plasma.

Ancillary Endpoints:

1. To compare the proportion and duration of SARS-CoV-2 PCR positivity (RT PCR) between the recipients of the anti-SARS-CoV-2 plasma and control plasma at days 0, 7, and 14.
2. To compare the levels of SARS-CoV-2 RNA between recipients of the anti-SARS-CoV-2 plasma and control plasma at days 0, 7, and 14.
3. To assess for genetic and transcriptomic differences at Day 0 (genomic) and Day 0,7,14 (transcriptomic) between the recipients of the anti-SARS-CoV-2 plasma and control plasma.

STUDY POPULATION

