1. To compare duration of need for supplemental oxygen and/or mechanical ventilation between recipients of the anti-SARS-CoV-2 plasma and control plasma.
2. To compare duration of hospitalization between recipients of the anti-SARS-CoV-2 plasma and control plasma.

3. To compare in-hospital and 28-day mortality between recipients of the anti-SARS-CoV-2 plasma and control plasma.

Ancillary Endpoints:

1. To compare the proportion and duration of SARS-CoV-2 PCR positivity (RT PCR) between recipients of the anti-SARS-CoV-2 plasma and control plasma at days 0, 7, and 14.
2. To compare the levels of SARS-CoV-2 RNA between recipients of the anti-SARS-CoV-2 plasma and control plasma at days 0, 7, and 14.
3. To compare genetic differences between recipients of the anti-SARS-CoV-2 plasma and control plasma to explore possible associations with poor outcome.
4. To compare transcriptomic differences between recipients of the anti-SARS-CoV-2 plasma and control plasma at Day 0, 7, and 14 to explore possible associations with poor outcome.

Definitions

Enrolled: From time consented to participate until designated as a screen failure or have either been discontinued from the study or completed it. II. Randomized: when a study arm is assigned. III. Screen Failures: signed informed consent, but then determined to be ineligible or withdraws before being randomized. IV. Discontinued: randomized, but then withdrawn by investigator or withdraws consent. V. Completed: Subjects are considered completed when they are followed through to day 28, if they die before day 28, or are discharged prior to day 14.

Study population

Inclusion Criteria for Enrollment 1. Willing and able to provide written informed consent prior to performing study procedures or having a legally authorized representative available to do so. 2. Age ≥ 18 years. 3. Evidence of SARS-CoV-2 infection by PCR test of nasopharyngeal swab or oropharyngeal swab/tracheal aspirate sample within 14 days of randomization 4. $\text{SpO}_2 \leq 94\%$ on room air or requiring supplemental oxygen, non-invasive or invasive mechanical ventilation at screening 5. Evidence of infiltrates on chest radiography 6. Females of childbearing age and males must be willing to practice an effective contraceptive method or remain abstinent during the study period.

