Subjects enrolled in the study will be randomized to receive study drug vs. control using a web-based randomization platform that will pre-generate all treatment assignments in a 2:1 ratio using random permuted blocks of random block sizes, stratified by country (US and Brazil) The assignment list is maintained by designated staff at the DCC, independent from the study, and then sent to the Principal Investigator/research team for each participant that is deemed eligible.

Study product considerations

The preparation of the anti-SARS plasma and the control plasma will take place at the New York City Blood Center and the CUIMC-NYPH Blood Bank will dispense the plasma products. The plasma collection procedures are not part of this research protocol and are described in separate protocols, which has separate IRB approval (AAAS9845). The description below provides a summary of study product considerations as context.

Collection:

All activities pertaining to the collection and processing of plasma will take place at [New York Blood Center/NYBC]. NYBC is one of the largest independent, community-based, nonprofit blood centers in the United States. NYBC has a longstanding research program and is well versed in the regulatory and ethical aspects of research, including clinical trials. The organization is FDA-licensed to produce convalescent plasma and AABB (American Association of Blood Banks) accredited, attesting to robust quality oversight of all operations. The donation and collection of donor convalescent plasma will occur under CUIMC IRB protocol AAAS9845.

Collection and processing:

- Standard apheresis plasma collection will be performed per routine standard operating procedure at the collection facility (NYBC). • As per routine practice, samples will be collected at time of donation for testing for transfusion-transmissible infections (all donors), ABO and red cell antibodies (all donors) and HLA antibodies (female donors with prior pregnancies). • Target collection volume: ~450-600mL; this will allow for later splitting (separation) into 200-250mL daughter units. • The plasma will be processed

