- Levels of SARS-CoV-2 RNA on Days 0, 7, and 14.
- Duration of need for supplemental oxygen and/or mechanical ventilation
- Duration of hospitalization
- Mortality.

Statistical Analysis

• Efficacy Objective

1. Primary Analysis, go/no-go decision, and power consideration

The primary analysis of the endpoint will be a one-sided nonparametric stratified Mann-Whitney test; stratification is done by country (US, Brazil). A “go decision” in this phase 2 trial will be a one-sided $P < .015$, suggesting evidence of promise of the treatment arm for further investigation in a phase 3 trial. Adaptive seamless phase 2/3: The results in this proof-of-concept study will be used to plan the sample size in a Phase 3 trial, which may include the data in this Phase 2 in the final analysis using adjusted P value as in a seamless phase 2/3 trial. Details of P value adjustment and sample size calculation will be decided before the final analysis of this study data.

The calculation was based on blinded pooled data of the Day 28 outcome and an odds ratio of 1.7 under a proportional odds assumption. With a 2:1 randomization ratio and a total sample size of 219 participants (146 in convalescent plasma vs. 73 control), a onesided Mann Whitney test at 15% level will have about 82% power to detect an odds ratio of 1.7. Since the difference in power between 219 and 220 is minimal, $N=219$ can be used to justify an enrollment total of 220. We note a recent study of antiviral drug yields an odds ratio of 1.15, with 95% CI: 0.67 to 1.96, which covers our assumed odds ratio.

2. Secondary and Ancillary Analyses

All secondary and ancillary efficacy analyses will also be intent-to-treat. With a sample size of 220, assuming 20% mortality up to day 28, we expect a total of 43 events. Longitudinal data collected over multiple days during the study period (e.g., PCR positivity, RNA) will be analyzed using the framework of generalized linear mixed model. Time-to-event variables (e.g., time to death) will be analyzed using Cox proportional hazards model. Continuous variables (e.g. duration of hospitalization) will be analyzed using Mann Whitney test. Treatment effects on these variables will be estimated with 95% confidence intervals.

3. Safety Analyses

Serious adverse events will be summarized by grades and types using proportions and 95% confidence intervals for the two study arms. Relative safety profile of the two arms will be compared using Fisher's exact test.

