Day 28 severity outcome on a seven-category ordinal scale consisting of the following categories: 1. Not hospitalized with resumption of normal activities 2. Not hospitalized, but unable to resume normal activities 3. Hospitalized, not requiring supplemental oxygen 4. Hospitalized, requiring supplemental oxygen 5. Hospitalized, requiring high-flow oxygen therapy or noninvasive mechanical ventilation 6. Hospitalized, requiring extracorporeal membrane oxygenation (ECMO), invasive mechanical ventilation, or both 7. Death

Virologic measures:

1. Rates and duration of SARS-CoV-2 PCR positivity (RT PCR) at days 0, 7 and 14.
2. Peak quantity levels of SARS-CoV-2 RNA at days 0, 7 and 14.

RISKS AND BENEFITS

Potential benefits of treatment

The potential benefits of antiviral treatment with anti-SARS CoV-2 plasma in patients with severe COVID-19 is unknown. However, based on available evidence from use of convalescent plasma in SARS-CoV-1 patients, shortened duration of illness and improved mortality are potential benefits.

Potential benefits of clinical monitoring and virologic testing

Subjects enrolled in the study will undergo close virological monitoring that may facilitate improved understanding of viral shedding that may have benefit to the individual, their family and the community at large.

Potential risks of study procedures

1. Risks of plasma: Fever, chills, rash, headache, serious allergic reactions, transmission of infectious agents
2. Transfusion related acute lung injury (TRALI) and transfusion related circulatory overload (TACO), both of which may worsen oxygen saturation and increase work-of-breathing
3. Risks of phlebotomy: local discomfort, bruising, hematoma, bleeding, fainting
4. Total blood draws will not exceed 500 mL
5. Risks of nasopharyngeal swab: local discomfort, vomiting
6. Risks of IV placement: bleeding, infection, thrombosis

Potential risks of genetic testing

Samples obtained for future research may include a search for genetic correlates of COVID-19 susceptibility or severity. Specimens will be labeled by study IDs, rather than names. This information will not be released to participants and will not become part of their medical records. Risks related to discrimination or other problems are deemed highly unlikely.

Alternatives

The alternative to participation in this study is continued standard-of-care clinical management.

Safety monitoring

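### The genetic ancillary objective compares randomized arms, a contrast that is null in expectation and does not match its stated purpose of relating genetics to outcome

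*Combined protocol and SAP*

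**What the plan says.** In the Investigational Plan, under Study Objectives, ancillary item 3 is "To compare genetic differences between recipients of the anti-SARS-CoV-2 plasma and control plasma to explore possible associations with poor outcome". Item 4 has the same structure for the transcriptome at Days 0, 7 and 14.

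The synopsis merges the two items into one: "To assess for genetic and transcriptomic differences at Day 0 (genomic) and Day 0,7,14 (transcriptomic) between the recipients of the anti-SARS-CoV-2 plasma" and control plasma. It keeps the comparison between arms, fixes genomics at Day 0 and omits the clause about outcome.

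The Randomization section says that the platform will "pre-generate all treatment assignments in a 2:1 ratio using random permuted blocks of random block sizes, stratified by country (US and Brazil").

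Under Risks and Benefits, the paragraph on genetic testing says that research on stored samples "may include a search for genetic correlates of COVID-19 susceptibility or severity".

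Under Statistical Analysis, the part on secondary and ancillary analyses names three methods. The first is: "Longitudinal data collected over multiple days during the study period (e.g., PCR positivity, RNA) will be analyzed using the framework of generalized linear mixed model". The others are a Cox model for time-to-event data and the Mann-Whitney test for continuous data. Genotype is not mentioned there or under missing data and non-compliance.

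**The concern.** The objective names one comparison (arm against arm) and gives the purpose of another (who does badly). Randomization is meant to remove any systematic relation between arm and patient characteristics that precede assignment. Genotype is such a characteristic, so a difference between arms in allele frequency can only reflect chance or selective sampling. Neither says which variants go with poor outcome. The Day 0 transcriptome is in the same position if it is sampled before infusion.

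An analyst who follows the sentence literally would run a test that cannot inform the question. The stored samples could address that question if they were analyzed by outcome. The stake is the usefulness of an exploratory component. The primary test, the go/no-go rule, the sample size and the safety analysis do not depend on it.

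**Working it through.** The plan gives no figure for the genetic objective, so there is none to reproduce. The check has four steps.

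**1. Is the contrast null?** Let G be the allele count and A the arm. G is fixed before A is drawn, and A is drawn at random 2:1 within country. Within each country, therefore, E[G | A = convalescent] − E[G | A = control] = 0. Because the ratio is the same in both countries, the overall difference is also zero in expectation, even if allele frequencies differ by country. Outcome does not enter this expression. The test's rejection rate therefore equals its level whatever the effect of G on outcome.

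**2. Numerical confirmation.** Input from the plan: "219 participants (146 in convalescent plasma vs. 73 control"), and 20% mortality. Assumptions that are not in the documents: allele frequency 0.1 or 0.3; per-allele odds ratio for death 1.0, 1.7 or 3.0; no treatment effect on death; one variant tested at two-sided 5%. The statistic is |r|·√(219 − 1), where r is the correlation of allele count with arm (the plan's contrast) or with death (the plan's purpose), compared with 1.96. Each scenario had 20,000 trials.

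| Allele frequency | Odds ratio per allele | Rejects: genotype vs arm | Rejects: genotype vs death |
|---|---|---|---|
| 0.1 | 1.0 | 4.8% | 4.8% |
| 0.1 | 1.7 | 5.0% | 33.0% |
| 0.1 | 3.0 | 5.0% | 87.1% |
| 0.3 | 1.0 | 4.8% | 4.9% |
| 0.3 | 1.7 | 5.1% | 56.0% |
| 0.3 | 3.0 | 4.9% | 98.8% |

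The simulation standard error at 5% is √(0.05 × 0.95 / 20,000) = 0.15 percentage points, so the arm column agrees with 5% throughout. The last column depends on the assumed frequencies and odds ratios, and it would fall under a threshold suited to many variants. The arm column would stay at whatever level is chosen.

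**3. How many patients could be contrasted by outcome?** The plan states: "assuming 20% mortality up to day 28, we expect a total of 43 events". Arithmetic: 0.20 × 220 = 44 deaths and 220 − 44 = 176 survivors. For N = 219, 0.20 × 219 = 43.8. The gap between 43 and 44 is immaterial. These counts are ceilings: Study Procedures makes stored samples conditional on feasibility at every visit where they are listed (Baseline, Days 1, 7 and 14).

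**4. Is the Day 0 transcriptome taken before treatment?** Stored samples are listed at the Baseline (Randomization) visit and not at the Day 0 infusion visit, and the Design Overview treats baseline as Day 0. The Day 0 sample therefore precedes infusion, and its between-arm contrast is also null in expectation. Days 7 and 14 follow infusion and can differ by arm.

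**The case against.** The strongest reply is that the drafting is loose but the intent is clear. Item 3 ends with a purpose about outcome, and the genetic-testing paragraph anticipates a search for correlates of severity. A genotype-outcome or genotype-by-treatment analysis was probably meant. No genotype test of any kind is specified, so no plan exists to run the uninformative one.

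Much of this stands. A reader might infer that every genetic finding from this trial will be a false positive and that the genetic question will go unanswered. The documents do not support that, because it would follow only if the literal contrast were the sole analysis run. It does not rescue the text, however. The only comparison written is between arms, the synopsis lacks even the purpose clause, and the statistical section supplies no outcome model to replace it. Nor does reading the contrast as a check of baseline balance fit the purpose stated in item 3.

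A reader might also extend the criticism to all of item 4. That is not supported: comparing arms at Days 7 and 14 is legitimate, and only Day 0 is affected.

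Finally, null means null in expectation. Chance imbalance can occur. Samples are taken only where feasible and the clinical team is unblinded, so selective sampling could also produce a difference between arms. That would be an artefact and would still not show an association with outcome.

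**Conclusion.** The point holds for item 3 and its synopsis counterpart, and for the Day 0 part of item 4. The written contrast has power equal to its test level for any genotype-outcome effect, and the plan gives no analysis that serves the stated purpose. This rests only on genotype preceding assignment and on assignment being random, both of which are clear from the documents. The power figures for the outcome analysis are illustrative. They show that such an analysis carries information that the arm contrast lacks, and they do not show that this trial would be adequately powered for a scan of many variants. The importance is low, because this is an exploratory ancillary item.

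**What to change.** **Item 3 and the synopsis.** Restate the objective as the association of recipient genotype with the Day 28 outcome, pooled across arms and adjusted for arm and country. Add a genotype-by-treatment interaction, labelled exploratory. State the multiplicity rule: which variants form the family, and which error rate is controlled.

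**Item 4.** Keep the comparison between arms at Days 7 and 14, with the Day 0 transcriptome as a baseline covariate and not as a between-arm endpoint. Test the association of the Day 0 transcriptome with outcome separately.

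**Statistical Analysis.** Add the exploratory model to the part on secondary and ancillary analyses, and report how many patients in each arm and outcome group have usable samples.

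**Cost.** Revised wording in two places, one exploratory model and a multiplicity rule. No new samples, assays or patients are needed, and the primary analysis does not change.
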